10.2 Shipping of Specimens

All samples must be labeled with the unique MSKCC CRDB participant study identification number and date of the specimen collection.

Frozen, banked PBMC samples are to be shipped on dry ice to MSK along with the appropriate Study Requisition Form to the address indicated on the form . Shipments should be made in batches every 3-6 months.

FFPE slides or blocks are to be shipped at ambient temperature to MSK along with the appropriate Study Requisition Form to the address indicated on the form . Shipments should be made in batches every 3-6 months.

Frozen purified DNA and RNA samples for sequencing are to be shipped on dry ice to UConn along with the appropriate Study Requisition Form to the address indicated on the form . Shipments should be made in batches every 2-4 weeks.

All participating sites will notify the MSK study coordinator when samples are shipped by completing and emailing the sample requisition form.

10.3 Future Unspecified Use of Biospecimens

The protocol includes an informed consent document and research authorization that meets statutory guidelines. Each participating site will have its own consent form meeting the requirements described in this section. The consent form will inform patients of the purpose of the bank, their rights in relation to it, and the safeguards in place to protect the confidentiality of their health information. The consent will state that some of the biospecimens will be saved to use for future research.

Type of future use

The consent specifically describes the types of future research that may be performed, including use of tissues to develop new drugs with cancer-associated molecular targets, development of cell lines, future use of cell lines to define cancer phenotype and (somatic) genotype, DNA sequence analysis of tumor compared to normal and identification of tumor-associated proteins as diagnostic or prognostic markers. It will be stated that researchers at MSK may either keep indefinitely or dispose of any leftover blood or tissues or other samples, including DNA that the samples contain. Blood and tissues will be stored with identifiers in secure tissue or fluid banks. It is stated that the samples could be lost or ruined because of mechanical failure, and that MSK cannot guarantee that samples will be stored indefinitely. The samples will be stored for as long as deemed useful for research purposes.

Consent for future use and re-contact

Patients are asked in a series of check boxes at the end of the consent if 1) they permit their biospecimen samples to be stored and used in future research to learn about or prevent cancer or side effects of treatment, or to develop new treatments; 2) if they permit their samples to be stored and used in future research to learn about, prevent, or treat diseases other than cancer; or 3) if they permit their samples, with personal identifiers protected, to be

used for research about inherited genetic factors, 4) if they permit their samples to be used for genetic analysis of the tumor and normal tissue to learn about the causes of cancer, 5) participants are asked if they agree to be contacted in the future as part of research studies for additional health information or to be asked to participate in future biospecimen research studies and 6) if they consent to be contacted to discuss research findings which may come from their sample. Finally, if not available (e.g. deceased), if they wish to have their designee designated on the consent to be contacted.

Participants will not be provided with specific results of research tests performed on their collected human biologic specimens.

Use of identifiable information for genetic studies

In the course of this research it is possible that some patients whose tumors are analyzed through investigational “next-generation” profiling in a research (non-CLIA) environment will be found to have somatic or germline mutations in genes that are known to be associated with an increased risk of cancer or other diseases. It will be stated in the consent that the participants will not receive any specific results from research tests. The consent will tell participants that if they wish to have genetic testing done for personal reasons than they should make an appointment with the MSK Clinical Genetics Service or Clinical Genetics Service at their site.

If in the course of this research a research finding is obtained that, in the opinion of the investigator, may be critical to the preventive care of the participant or their family, the investigator can communicate that finding to the MSK IRB Genomic Advisory Panel (GAP). The finding will be reviewed by the GAP to determine whether the incidental finding should be discussed with the participant. For MSK patients, in the event that the GAP determines that the finding should be discussed with the participant, and the participant has consented to be re-contacted, then the treating/consenting physician shall be contacted by the panel and asked to refer the participant to the Clinical Genetics Service for further discussion of the research finding.

The following information must be provided to GAP for review:

- Participant Name/MRN #
- Type of Biospecimen (tissue, blood, saliva)
- Incidental Finding
- Collection Protocol #
- Contact: [contact]

For non-MSK patients being treated at one of the participating institutions, if the GAP determines the finding to be reportable to the participant and the participant has consented to be re-contacted, results will be returned to the Site Principal Investigator via the study team. Site policies on returning these research findings to the patient should be followed.

We anticipate that other research assays may be incorporated into this protocol as technology evolves.

Voluntariness of research participation

It is stated that taking part in this tissue and blood bank is voluntary and patients have the right to withdraw at any time. Participation in the study will not impact on the clinical care patients receive.

Withdrawal

Participants may decide at a later date that they do not want identified blood and tissue samples to be stored in the tissue bank and /or used for future research. If participants decide to withdraw from the study, specimens that have not yet left the specimen archive will not be used in new studies and any remaining portions of samples that have not been used for research will be used only for clinical purposes or, if requested by the patient, destroyed. For specimens already shipped out from the archive, it may not be possible to locate the samples or stop already ongoing research. The withdrawal request will be documented in CRDB and the system updated accordingly. In addition, a note-to-file documenting the patient withdrew must be filed in his/her medical records.

Rights after death

The consent states that if the research participant dies or is unable to make his/her wishes known, all of their rights to decide about future uses of the blood or tissues will pass to the authorized representative of the estate. If there is no representative of the estate, the rights pass to the next of kin.

Risks of research participation

The greatest risk is release of information from health or research records in a way that violates privacy rights. MSK and any participating sites will protect records so that name, address, phone number, and any other information that identifies the participant will be kept private. It will be stated to the participant that the chance that this information will be given to an unauthorized individual without the participant's permission is very small.

Costs/compensation

There is no cost to the participant to enroll in this research. Tissue or blood obtained in this research may be used to make a cell line, and these may be patented or licensed and thus may have significant commercial value. The participant is informed that there are no plans to provide financial compensation for use of their human biologic specimens, nor are there plans for the participant to receive money for any new products, tests, and discoveries that might come from this research.

Biospecimen Privacy

Medical information is confidential. The participant's personal identity will not be used in reports that are written about the research. The MSK IRB/PB will review all requests for research performed involving biospecimens ascertained through this protocol. Blood and tissue samples may be stored with a code linked to the patient's medical record. The results of any research using blood or tissues will not be placed in the medical record.

The consent indicates that samples and genetic information collected may be shared with other qualified researchers and placed in online databases. An example of an online database is the NIH dbGAP database, which is monitored by the National Institutes of Health, and may be made accessible to investigators approved by the U.S. government. Such information will not include identifying information such as name. It is also stated in the

Research Authorization (HIPAA Authorization) that research data (e.g. genomic sequence) may be shared with regulators. The requirements for submission of genotype/phenotype data into the NIH dbGAP or any other public database will be followed as per the IRB SOP for Genomic Data Sharing.

Use of banked samples (at MSK)

When samples are to be analyzed, the individual investigator needs to write an IRB biospecimen protocol. This protocol is fast-tracked through MSK Research Council review and is reviewed at the MSK IRB by the expedited review process. This protocol is only for research that will be done on biospecimens obtained under identified protocols and their informed consent and research authorization that include the institutional future use questions. The consent and research authorization for the use of the biospecimens will be waived as per 45 CFR 46.116(d) and 45 CFR 164.512(i)(2)(ii).

11.0 TOXICITIES/SIDE EFFECTS

Anticipated Toxicities for Ipilimumab and Nivolumab and detailed in the attached Investigators Brochures provided by BMS.

11.1 Definition of an Adverse Event

An Adverse Event (AE) is any untoward medical occurrence in a patient administered the study intervention, which does not necessarily have a causal relationship with the treatment. An AE can therefore be any unfavorable and/or unintended sign, symptom, or disease temporally associated with the use of a medicinal product, whether or not considered related to the study intervention. AEs may also include pre- or post-treatment complications that occur as a result of protocol specified procedures, lack of efficacy, overdose, or drug abuse/misuse reports, or occupational exposure. Preexisting events that increase in severity or change in nature during or as a consequence of participation in the clinical study will also be considered AEs.

An AE does not include the following:

- Medical or surgical procedures such as surgery, endoscopy, tooth extraction, and transfusion. The condition that led to the procedure may be an AE and must be reported.
- Pre-existing diseases, conditions, or laboratory abnormalities present or detected before the screening visit that do not worsen
- Situations where an untoward medical occurrence has not occurred (e.g., hospitalization for elective surgery, social and/or convenience admissions)
- Overdose without clinical sequelae
- Any medical condition or clinically significant laboratory abnormality with an onset date before the consent form is signed and not related to a protocol-associated procedure is not an AE. It is considered to be pre-existing and should be documented as part of the patient's medical history.

Adverse event reporting will be performed in accordance with institutional guidelines for reporting to each participating sites local IRB. Toxicities and laboratory abnormalities will be assessed according to CTCA 4.0. All toxicities that meet criteria of Grade 2 or higher, regardless of causal relationship to nivolumab and/or ipilimumab, will be reported to MSK. Grade 1 toxicities unrelated to study drug will not be required to be reported. Any toxicity related to study drug will be reported to MSK. All serious adverse events will be reported to both MSK and to BMS in accordance with guidelines outlined in section 17.2.1.

12.0 CRITERIA FOR THERAPEUTIC RESPONSE/OUTCOME ASSESSMENT

Patients are considered evaluable for the primary and secondary endpoints if adequate sequencing data is generated from pre-study biopsy material to determine mutation burden/neo-antigen score.

Responses will be assessed by RECIST 1.1.

Additional clinical endpoints will be evaluated in an exploratory manner.

Duration of Response (DOR) Duration of Response will be determined for each patient with time origin at the first occurrence of confirmed response (CR,PR) until the first occurrence of confirmed progression or date of death if the patient dies due to any causes before progression. Every effort will be made to follow patients for progression after they discontinue the study.

Progression-free Survival (PFS) Progression-free Survival will be determined for each patient with time origin at the start of the treatment (day 1) until the first occurrence of confirmed progression or date of death if the patient dies due to any causes before progression. If a patient does not progress and is still alive, they will be censored on the date of last follow-up. Every effort will be made to follow patients for progression after they discontinue the study.

Overall Survival (OS) Overall survival (OS) will be measured for each patient with time origin at the start of the treatment (day 1) until recorded date of death. If a patient is still alive, they will be censored on the date of last follow-up. Every effort will be made to follow patients for overall survival after they discontinue the study.

Patient Evaluation & Statistics

All patients who receive at least one dose of nivolumab will be evaluated for tumor response (ORR, DOR), including patients who (1) develop rapid symptomatic disease progression, or (2) drop out early due to death or treatment-related toxicities. All patients who received at least one dose of nivolumab will be included in the clinical efficacy analyses of PFS and OS. Kaplan-Meier methodology will be implemented to estimate the median OS and PFS.

Of note, atypical responses are well known to occur in patients treated with immune checkpoint blockade, including early radiographic progression due to immune infiltration followed by subsequent radiographic response and durable clinical benefit. Thus, patients who

have early radiographic progression but are felt to be clinically benefitting and convert to confirmed stable disease, partial response, or complete response will be considered progression-free and will be assigned a best confirmed overall response of SD, PR, or CR.

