2.0 OBJECTIVES AND SCIENTIFIC AIMS

Primary Correlative Objective: Obtain preliminary prospective data on whether mutational load is associated with RECIST 1.1 response to immunotherapy.

Primary Clinical Objective: Obtain prospective data on the overall response Rate (per RECIST 1.1) to 1) nivolumab monotherapy and 2) ipilimumab and nivolumab combination therapy in patients progressing on initial nivolumab monotherapy.

Secondary Clinical Objectives:

1. Evaluate duration of response (DOR), progression free survival (PFS), overall survival (OS), rate of grade 3/4 toxicity.
2. Evaluate ORR, DOR, PFS, OS according to the immune related RECIST criteria.

Secondary Correlative Objectives:

1. Obtain preliminary prospective data on whether neo-antigen score is associated with RECIST 1.1 response to immunotherapy.
2. Compare tumor characteristics (mutation burden, neo-antigen score, PD-L1, TCR repertoire, immune infiltrate) between pre-treatment and on-treatment (optional) tumor biopsies.
3. Evaluate tumor PD-L1 expression across range of mutation burden/predicted neo- antigens.
4. Evaluate TCR repertoire across a range of mutation burdens/predicted neo-antigen scores.
5. Evaluate for the presence of predicted neo-antigen specific T cells in peripheral blood samples.
6. Compare IMPACT assay to whole exome sequencing for the evaluation of patients according to mutation burden.

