4.0 OVERVIEW OF STUDY DESIGN/INTERVENTION

4.1 Design

The study design will include 2 independent study populations (melanoma and bladder). The bladder cohort will be analyzed for the primary and secondary endpoints. The melanoma cohort will be analyzed in a descriptive fashion. All patients enrolled on study who meet eligibility criteria, including pre-study biopsy, will be treated as described in section 4.2. Tumor biopsy material will be used for whole exome sequencing and whole transcriptome sequencing to evaluate the tumor mutation burden and neo-antigen score for each individual patient/biopsy sample.

Statistical Plan for Evaluation of Primary and Secondary Objectives

Patients who receive at least 1 dose of nivolumab will be considered evaluable for the primary clinical objective and patients who have adequate biopsy material for whole exome sequencing and adequate sequencing data for determination of mutation burden will be considered evaluable for the primary correlative objective (1). Tumor mutation burden and neo-antigen score will be determined for each patient enrolled as described in Appendix 3.

The primary clinical objective is to determine the confirmed objective response rate defined as the proportion of patients who achieve a complete or partial response to protocol therapy. The primary correlative objective is to obtain information on mutational load and obtain preliminary prospective data on whether this factor is predictive of response to immunotherapy. Patients mutational load will be assessed using tissue obtained prior to treatment and the number of mutations will be calculated. We will perform a nonparametric receiver operator characteristic (ROC) curve analysis with mutational load as a continuous measure and estimate the area under the curve (AUC) to assess the detectability of responders. ***This will allow us to prospectively test the hypothesis that a higher mutational burden is associated with a higher likelihood of response and also estimate the strength of the relationship between mutational burden and response rate.***

Patients who develop early clinical progression or death related to disease progression (i.e. before initial imaging) will be evaluated as non-responding patients for the purpose of study

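### Section 12 makes adequate sequencing a condition for the primary endpoints, against the all-dosed rule for ORR; Section 4.1 separately drops early losses that the all-dosed rule keeps

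*Combined protocol and SAP*

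**What the plan says.** Section 4.1 defines two populations. For the clinical objective, "Patients who receive at least 1 dose of nivolumab will be considered evaluable for the primary clinical objective". The same sentence ties usable biopsy and sequencing data to the primary correlative objective only.

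Section 12 begins with a different rule: "Patients are considered evaluable for the primary and secondary endpoints if adequate sequencing data is generated from pre-study biopsy material". The sentence goes on to say what the data are for, "from pre-study biopsy material to determine mutation burden/neo-antigen score", and names no subset of endpoints. Further down, under its patient evaluation heading, the same section says "All patients who receive at least one dose of nivolumab will be evaluated for tumor response (ORR, DOR". Section 14 again assigns the primary clinical endpoint to everyone with at least one nivolumab dose. It adds a sentence describing patients who are both dosed and successfully sequenced as evaluable for the clinical and the correlative objectives.

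On early events, Section 4.1 states that "Patients who develop early clinical progression or death related to disease progression (i.e. before initial imaging) will be evaluated as non-responding patients". It then says that a patient lost in the first 12 weeks is non-evaluable if response cannot be determined from imaging, clinical progression or disease-related death. It calls this scenario unlikely. Section 14 classes early dropout through death as progressive disease in one place and as non-response in another, with no restriction on cause.

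**The concern.** A dosed bladder patient whose biopsy fails sequencing is in the ORR denominator under three statements and outside it under the first sentence of Section 12. A dosed patient lost early without a determination is inside under the same three statements and outside under the later rule in Section 4.1.

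The two exclusions act differently. Someone with no response determination cannot be a confirmed responder, so removal takes one from the denominator and nothing from the numerator. Sequencing failures may include responders, so removing them biases the ORR only if failure is related to response, and then in either direction.

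The trial is open label and not randomised, and ORR is its primary clinical result. The denominator should not be open to choice once responses are known.

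**Working it through.** **Inputs.** From Section 14: 71 bladder and 10 melanoma patients; about 10% biopsy or sequencing failure; about 5% clinical failure, which includes replaced patients; about 85% jointly evaluable; response rates of 25%, 33% and 50% in the power statement. Assumptions made here: all 71 bladder patients are dosed, and the two kinds of failure do not overlap (as 85% implies).

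**The plan's own figures.** 71 × 0.85 = 60.35, the stated 60 or so bladder patients; 10 × 0.85 = 8.5, against about 8 stated. With n = 60, a two-sided 5% test of AUC against 0.5 and a binormal variance, power is 79.6%, 78.5% and 78.9% for AUC 0.70, 0.71 and 0.73. The plan states 80% and does not give sidedness. These figures properly rest on sequenced patients, so the ORR denominator does not enter them.

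**Early losses.** Responders: 71 × 0.25 = 17.75, taken as 18; 71 × 0.33 = 23.4, taken as 23; 71 × 0.50 = 35.5, taken as 36. Losses: 1 to 4. The upper value comes from 71 × 0.05 = 3.55, rounded up; it spends the whole clinical-failure allowance. ORR = responders / (71 − losses).

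| Responders | All dosed | 4 removed | Shift (points) |
|---|---|---|---|
| 18 | 18/71 = 25.4% (exact 95% CI 15.8 to 37.1) | 18/67 = 26.9% (16.8 to 39.1) | +1.5 |
| 23 | 23/71 = 32.4% | 23/67 = 34.3% | +1.9 |
| 36 | 36/71 = 50.7% | 36/67 = 53.7% | +3.0 |

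With 18 responders and 1 removed, 18/70 = 25.7%, a shift of +0.4.

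**Sequencing condition.** About 71 × 0.10 = 7.1, so 7, are removed, leaving 64. If failure is unrelated to response, the expected number of responders among the 7 is 7 × 18/71 = 1.77, and (18 − 1.77)/64 = 25.4%, as before. If none of the 7 responded, 18/64 = 28.1%; if 4 did, (18 − 4)/64 = 21.9%. When failure is unrelated to response, these two splits have hypergeometric probabilities C(53,7)/C(71,7), about 12%, and C(18,4) × C(53,3)/C(71,7), about 5%. Fewer than 7 are affected if some failures occur before dosing.

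**The case against.** The strongest reply is that the intended ORR population is clear. Three statements give the all-dosed rule, one of them in the biostatistics section, and Section 4.1 separates the clinical and correlative populations in a single sentence. On that view the opening of Section 12 merely lacks the word correlative. This stands as to intent and makes the repair easy, but the sentence as written still covers the primary clinical endpoint.

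The early-loss rule can be read as a narrow exception to the all-dosed rule. It speaks of a patient on study, so that the patient was dosed is an inference. A reader might say that the plan is silent on how early losses count; it is not, because Section 4.1 assigns them a status. The fault is that this status conflicts with the unqualified all-dosed statements and favours a higher ORR. Declaring the exception openly would remove the inconsistency but not that direction.

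Other, stronger readings are not supported:

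- Section 14's sentence on dosed and sequenced patients might be taken as a second contradictory rule. It fits the joint clinical and genomic set of about 60 and needs only clearer wording.
- Early deaths from causes other than the cancer might seem unclassified. Section 4.1 is silent on them, but Section 12 includes early deaths in the response evaluation and Section 14 classes them without regard to cause.
- The conflict might be extended to DOR, PFS and OS. Section 2 lists them as secondary ("Evaluate duration of response (DOR), progression free survival (PFS), overall survival (OS), rate of grade 3/4 toxicity"), but Section 12 says "Additional clinical endpoints will be evaluated in an exploratory manner" and, like Section 14, uses all dosed patients. Any conflict depends on which label applies.

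Finally, Section 4.2 reports that patients in active follow-up are coming off study before closure, so a change now could follow knowledge of outcomes. That has little force here, because the correction returns to a rule already stated three times.

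**Conclusion.** The point holds for ORR. The opening of Section 12 contradicts the all-dosed rule, and the early-loss rule in Section 4.1 conflicts with it for any dosed patient. If all 71 bladder patients are dosed, removing 1 to 4 early losses raises the ORR by 0.4 to 1.5 points at 18 responders, and by about 3 points at a 50% response rate with 4 losses. These shifts are small beside the confidence interval, and the plan expects such losses to be rare. The sequencing condition causes no expected shift if failure is unrelated to response, and a shift of either sign if it is related.

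A reader might infer that the sequencing condition inflates the ORR, or that the power statement is undermined. The documents support neither: the direction of any sequencing effect is unknown, no ORR threshold is set, and the AUC calculation correctly uses sequenced patients. This should be fixed because it concerns a primary endpoint and the repair is simple, not because the numbers move far.

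**What to change.** 1. In the first sentence of Section 12, limit the sequencing condition to the mutation-load and neo-antigen analyses. Reword the matching sentence in Section 14 so that it plainly describes the joint clinical and genomic set.
2. In Section 4.1, state that a dosed bladder patient with no response determination stays in the ORR denominator as a non-responder. If an evaluable-patient ORR is wanted, label it supportive and make these exclusions only there.
3. As a minor alignment, make the early-death wording in Section 4.1 match Section 14.

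The cost is wording only. Accrual and the AUC calculation do not change. The reported ORR may be slightly lower than an evaluable-only figure, by the amounts shown above.
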